Primary	Objectives To investigate the potential of retinal imaging technology to assess endothelial function in women during pregnancy, in order to evaluate the effect of GH on maternal CV function.	Outcome Measures Primary Outcome Measures: 1. Retinal Vascular System 2. Endothelial Function 3. Cardiovascular Function biomarkers Secondary Outcome Measures: 1. Pregnancy-Related Health Outcomes 2. Maternal Health
Secondary	Objectives Study – Aim: Investigate whether retinal imaging is able to capture endothelial dysfunction in women who have complicated pregnancy. Endothelial function measured using retinal imaging and ultrasound pulse-wave Doppler and measured in correlation with serum biomarkers.	Outcome Measures 1. Primary Outcome Measures - Retinal Vascular Health measurements - Ultrasound Pulse-Wave Doppler Findings - Blood Biomarkers 2. Secondary Outcome Measures - Long-term Cardiovascular Risk Indicators
Optional Inclusion Criteria	Prospective imaging study 1- Women aged 18 or above 2- Women who are pregnant after 8 weeks 3- Women must be able to give written informed consent (ICF) Note: Women that are diagnosed with gestational hypertension (after 12 weeks) will be included. Includes the following hospital: NINEWELLS HOSPITAL	
Optional Exclusion Criteria	1- Maternal age less than 18 years 2- Women who are not capable of giving informed consent (ICF).	

Studying Pregnancy's VAscular and Retinal Changes (SPARC), Non CTIMP Protocol (SPARC) During Preg <v1.0 13/3/2025>; IRAS: 347685

5.Known retinal or eye disorders	 3- Pre-existing chronic hypertension or cardiovascular diseases diagnosed prior to the index pregnancy. 4. Women that have chronic hypertension at their booking visit (before 12 weeks)
hypertensive therapy, anticoagulants).	5.Known retinal or eye disorders6. Use of medications affecting endothelial function (e.g., ongoing anti-

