3.12 STUDY POPULATION

Our study populations are defined as follows

The study design is prospective study. All pregnant women will be included at the start except for exclusion criteria see (3.15). Outcome of pregnancy will be documented and participants will be placed into one of two groups retrospectively:

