3.14 INCLUSION CRITERIA

Case group:

Women who

- Are Aged 18 or above
- Are Able to give written informed consent (ICF)
- Are in mid-to-late gestation.
- Were diagnosed with Gestational hypertension (systolic BP ≥ 140 mmHg or diastolic BP ≥ 90 mmHg) in their pregnancy.
- Do not have cardiac or ophthalmic disorders

Control group:

Pregnant women that are

- Aged 18 or above
- Able to give written informed consent (ICF)
- Have no gestational hypertension (normal pregnancy/ nonhypertension)
- Do not have cardiac or ophthalmic disorders

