3.15 EXCLUSION CRITERIA

Exclusion criteria are the same for both case and control groups:

Case group:

Women who

- Women with ophthalmic disorders
- Women who have hypertension during pregnancy
- Maternal age less than 18 years at delivery.
- Women who are not capable of giving informed consent (ICF).
- Individuals participating in the clinical phase of another interventional study or have done so within the last 30 days (unless they are participating in the follow-up phase of another interventional trial/study, or who are enrolled in an observational study, will be co-enrolled where the CIs of each study agree)

Control group:

- Women with any history of gestational hypertension (systolic BP ≥ 140 mmHg or diastolic BP ≥ 90 mmHg))
- Women with ophthalmic disorders
- Women who had hypertension prior to pregnancy
- Maternal age less than 18 years at delivery.
- Women who are not capable of giving informed consent (ICF).
- Individuals participating in the clinical phase of another interventional study or have done so within the last 30 days (unless they are participating in the follow-up phase of another interventional trial/study, or who are enrolled in an observational study, will be co-enrolled where the CIs of each study agree).

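### The case-group exclusion list in section 3.15 rules out the hypertensive women that section 3.14 requires as cases, and its two lists differ although it says they are the same

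*Protocol*

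**What the plan says.** Section 3.14 makes the diagnosis a condition of being a case: the woman must be one of those who "Were diagnosed with Gestational hypertension (systolic BP ≥ 140 mmHg or diastolic BP ≥ 90 mmHg) in their pregnancy". The synopsis agrees in a note to its inclusion criteria: "Women that are diagnosed with gestational hypertension (after 12 weeks) will be included". Section 3.2 names the Hypertension Clinic as a recruitment source, and section 6.1 says that newly diagnosed women attending such clinics will be recruited.

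Section 3.15 opens with "Exclusion criteria are the same for both case and control groups" and then prints two lists. The case list contains "Women who have hypertension during pregnancy". The control list does not contain that line. It has "Women who had hypertension prior to pregnancy" instead, which is absent from the case list.

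The synopsis has a single exclusion list, not divided by group. Item 3 is "Pre-existing chronic hypertension or cardiovascular diseases diagnosed prior to the index pregnancy", and item 4 concerns "Women that have chronic hypertension at their booking visit (before 12 weeks" of gestation. Item 6 excludes women on medication that affects endothelial function, with ongoing antihypertensive therapy as an example.

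Section 3.12 sends the reader to 3.15, not to the synopsis, for exclusions: "All pregnant women will be included at the start except for exclusion criteria see (3.15". Section 9.1 defines gestational hypertension as new onset after 20 weeks, and chronic hypertension as present before pregnancy or before the 20th week.

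**The concern.** The study compares women with gestational hypertension with women without it. The rule that forms the first group therefore has to be one that a woman can satisfy. As printed, the defining feature of a case is also a reason to exclude her. Section 3.15 is the list that 3.12 points to, and section 4.1 has candidates screened against the inclusion and exclusion criteria by telephone or email, so this is working text for the staff who screen.

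Two things are at stake. If staff follow 3.15, the case group cannot be filled and the primary comparison cannot be made. If they set the line aside, each case enrolled departs from the approved protocol, and section 11.1 requires deviations to be recorded and sent to the Sponsor as potential breaches.

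The mismatch between the two lists adds to this. A reader who relies on 3.15 alone finds hypertension before pregnancy excluded for controls but not for cases, contrary to the section's opening sentence and to the synopsis.

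**Working it through.** **The planned number of cases.** Inputs from section 6.1: about 4500 births a year, about 450 with gestational hypertension, 110 women to be recruited. Input from section 3.13: 11 cases.

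- Rate: 450 / 4500 = 0.10.
- Expected cases: 110 × 0.10 = 11, which reproduces the plan's figure.

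**Reading 1: the line applies to membership of the case group.** Section 3.12 assigns women to groups retrospectively, once the outcome is known. Every woman who meets 3.14 has had hypertension in the pregnancy, so every one meets the 3.15 exclusion. Eligible cases: 11 − 11 = 0.

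**Reading 2: the line applies only at entry.** A woman who is normotensive when enrolled and develops gestational hypertension later would not be excluded. A woman already diagnosed when screened would be. Let m be the number of the 11 cases diagnosed before entry. The cases left are 11 − m. The protocol does not give m, so the possible range is 11 (m = 0) down to 0 (m = 11). Sections 3.2 and 6.1 plan to recruit newly diagnosed women, so m is intended to be above zero and the contradiction remains.

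**The lists side by side.**

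| Point | Synopsis | 3.14 / 3.15, cases | 3.15, controls |
|---|---|---|---|
| Gestational hypertension in this pregnancy | Included | Required by 3.14; any hypertension during pregnancy excluded by 3.15 | Excluded |
| Hypertension before pregnancy | Excluded for all | Not listed | Excluded |
| Chronic hypertension at booking, before 12 weeks | Excluded for all | Not listed separately | Not listed separately |
| Ongoing antihypertensive therapy | Excluded for all (item 6) | Not listed | Not listed |

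**The time boundary.** The synopsis excludes chronic hypertension found before 12 weeks and includes gestational hypertension diagnosed after 12 weeks. Section 9.1 places the division at 20 weeks. A woman first found hypertensive at, for example, 16 weeks can be included as gestational hypertension under the synopsis but is chronic under 9.1. Simply copying the synopsis wording into 3.15 would carry this conflict with it.

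**The case against.** The best defence is that the line is a drafting slip, probably for the prior-hypertension line in the control list. The synopsis note, 3.14, 3.2 and 6.1 all show that women with gestational hypertension are wanted, and a sensible team would not turn them away. That is the likelier explanation of how the line arose, but it does not cure it: 3.15 is the list to which 3.12 refers, and working round it means departing from the approved text. It is also fair to say that a count of zero is not the only reading. The entry-only reading keeps women who are diagnosed later, but still loses those already diagnosed.

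A reader might go further and infer that, once the impossible line is ignored, the case group is open to women with long-standing hypertension while controls are protected, so that vascular changes predating pregnancy would be counted as an effect of gestational hypertension. The documents do not support this for the protocol as a whole:

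- Synopsis items 3 and 4 bar pre-existing and booking-visit chronic hypertension for all participants.
- The 3.14 criterion is a diagnosis of gestational hypertension, with the blood pressure values in brackets. Section 9.1 defines that diagnosis as new onset.
- Read literally, the disputed line excludes chronic hypertensives too.

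The omission of prior hypertension for cases is thus a fault within 3.15, not a policy of the protocol. Nor can a bias be sized: the documents give no basis for how many chronic hypertensives might enter or how far their measurements would differ.

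**Conclusion.** The contradiction stands and should be corrected. The case-group exclusion in 3.15 conflicts with 3.14, with the synopsis and with the recruitment described in 3.2 and 6.1. Its size is exact under the literal reading: 0 eligible cases against 11 planned. Under the entry-only reading it is the loss of every case diagnosed before entry, a number the protocol does not state. Separately, the two 3.15 lists are not the same, contrary to the section's own opening, and the case list omits a prior-hypertension exclusion that the synopsis applies to everyone.

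The conclusion needs no statistical assumption, only the text as printed. It rests on the contradiction alone and does not extend to a claim of confounding by chronic hypertension.

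**What to change.** 1. In 3.15, remove or correct the case-group line on hypertension during pregnancy so that it no longer contradicts 3.14.
2. State the exclusion for hypertension before pregnancy for both groups, in line with the undivided list in the synopsis. Where the two 3.15 lists are meant to differ, amend the opening sentence to say so.
3. Reconcile the synopsis, 3.14, 3.15 and 9.1 on the boundary between chronic and gestational hypertension (12 weeks in one place, 20 weeks in another). The investigators should decide which applies and use it throughout.
4. Decide explicitly whether synopsis item 6 is meant to apply to cases. Carried into 3.15 unchanged, it could remove women treated for gestational hypertension. Left out, the synopsis and 3.15 still disagree.

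The cost is a short text amendment with the Sponsor, ethics committee and NHS R&D approvals that section 11.1 requires. It needs no new measurements. Whether the recruitment target is affected depends on step 4, because excluding treated women would reduce the yield of cases. The protocol does not say whether recruitment has begun. If it has, women already screened should be checked against the reconciled criteria.

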4 PARTICIPANT SELECTION AND ENROLMENT

For the following reasons, there is very little chance of researcher bias: 1. Objective examinations are used to measure the vascular function in pregnancy non-invasively; the majority of these tests are automated. 2. The woman's own attending clinicians will diagnose pregnancy problems, like PE, gestation hypertension and gestation diabetic mellitus based on the hospital's established criteria.

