3.1 INTERVENTION

- Retinal imaging
- Blood sample (sFlt-1 &PLGF (clinically used to diagnose PE), endothelin-1 (marker of endothelial dysfunction))
- Ultrasound
 - Carotid
 - Ophthalmic artery doppler

Retinal imaging and ultrasound (including carotid and ophthalmic artery Doppler) will be conducted in the Tayside Clinical Research Centre/Clinical room at the Division of Cardiovascular Research (Blood Flow Lab), Ninewells Hospital, by PI, [name].

Blood samples will be collected by nurses in the Clinical Research Centre (CRC). All procedures will be completed on the same day as the examination.

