3.2 STUDY RECRUITMENT

Women will be recruited who are pregnant for assessment in mid and/or late term. The outcome of the pregnancy will be tracked.

Women will be invited to join the study by the care teams in clinics at Ninewells and the Tayside area

- Obstetric Antenatal Clinics (Recruitment will be overseen [name] [name] (UoD/NHS) and [name] (NHS))
- Assisted conception clinic (Recruitment will be overseen [name] [name] (UoD/NHS))
- Hypertension Clinic (Recruitment will be overseen by [name](UoD/NHS))

This is a prospective study. Control groups will be made up of women that do not get gestational hypertension. Pregnant women that attend the Hypertension clinic may be recruited due to their gestational hypertension. Women attending the Obstetric Antenatal Clinics and Assisted conception clinics will be identified with clinical collaborators including [name] [name], [name] and [name]. To be able to identify potential participants from their medical records Caldicott Approval will be sought. Only with Caldicott approval will the medical records be searched.

The care team will approach or invite participation in the study in clinic. Any invitation will introduce the potential patient to the study team and will include a PIS. The care team will not follow up with patients to determine their interest in the study.

The study team will include Clinical Research Centre nurses that will assist with recruitment. The study team will confirm recruitment via a short telephone conversation prior to them attending Ninewells for the study visit.

Advertisement of the study and identification of potential participants will be identified from the NHS Tayside clinics at Ninewells Hospital including maternity clinics, ultrasound department, antenatal clinics, day assessment unit, Assisted Conception Unit, https://www.acudundee.org/ hypertension and diabetics clinics among others. Caldicott approval will be gained to allow identification of potential participants from medical records and clinical lists by the care team. Letters with PIS may be sent to the potential participants from the clinical team. We chose the following sites, since this is where pregnant women obtain their routine care.

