3.4 STUDY FLOWCHART

3.5 STUDY MATRIX

Example Study Matrix

	Recruitm ent	Week 10 (+/-3wk)	Week 20 (+/-3wk)
Recruitment	V1	n/a	n/a
Cardiovascular assessment		X	X
Blood sample		X	Χ
Blood processing		X	Χ

On the same day as the blood sample, carotid artery doppler, and retinal imaging, an ophthalmic artery Doppler will be conducted. In the unlikely event that this is not possible, the ophthalmic artery doppler will be finished in 7 days.

We aim to image women up to 2 times; at 10 and 20 weeks (+/- 3 weeks) in line with their routine clinical care. However, we will accept only one visit at either of the timepoints.

STUDY ASSESSMENTS

Retinal imaging

Retinal imaging is a basic ophthalmic imaging technique which takes a photo of blood vessels at the back of the retinal. The participant needs to open her eyes and stare straight ahead at an object while the image is taken and uploaded to a computer.

Doppler Ultrasound

The ultrasound is a painless, safe test that uses sound waves to make images of the region of interest. Two regions will be examined in this study, which are Ophthalmic and Carotid region.

OPHTHALMIC ARTERY DOPPLER

The participant will be positioned in a supine position and will rest for 5 minutes. Subsequently, an ultrasound probe with sterile conduction gel will be applied to her closed upper eyelid. A quick 2D scan will be undertaken to identify anatomical features of the eye, including the optic nerve, visible as a hypoechoic band, which will be utilised as a reference. The ocular artery will be identified using colour flow, specifically in the superior and medial regions of the artery, around 15 mm behind the optic disc. Subsequently, pulsed-wave Doppler will be employed to document three to five similar waveforms.

To reduce any potential negative impact on the eyes and adhere to the ALARA ("as low as reasonably achievable") guideline, the study will be conducted in under 2 minutes per eye. Both eyes will be imaged.

CAROTID ULTRASOUND

During the test, gel is applied to the side of the neck to help the sound waves travel effectively. While lying down, a small scanner is gently placed on the skin of the neck to take the necessary pictures. This procedure is safe and may cause some pressure, but not pain, as the device moves on the neck.

The elasticity of the blood vessels will also be measured. A small pen-like device will be placed gently on the neck and at the same time a cuff is placed on the thigh (over your clothes).

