5.1 DATA COLLECTION

The patients will be given an identification number to ensure anonymity. Data collected will include age, previous medical history, medications, diagnosis, treatment, blood report findings, and personal history. This clinical data will be used in the analysis of results and will be used to correlate with the findings of the CV assessments. The data will be collected by the research team on a paper Case Record Form (CRF), which will not hold any name, initials, and CHI, with subsequent transcription into an Excel database. Electronic storage will be in an encrypted form on a University of Dundee password-protected device. Study assessments will be conducted by the PI and a trained research member of the team under the supervision of the CI.

On the same day as the blood sample, carotid artery doppler, and retinal imaging, an ophthalmic artery Doppler will be conducted. In the unlikely event that this is not possible, the ophthalmic artery doppler will be finished in 7 days.

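### Section 4 claims little risk of researcher bias, but its reasons do not cover measurement: women with known gestational hypertension may be scanned, and nothing masks the reading of images and waveforms

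*Protocol*

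**What the plan says.** Section 4 asserts that "there is very little chance of researcher bias" and gives two reasons. The first is that the examinations are objective and that "the majority of these tests are automated". The second is that "The woman's own attending clinicians will diagnose pregnancy problems", using the hospital's own criteria.

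Other sections describe how the measurements arise:

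- **Who is scanned.** Section 3.2 says "Pregnant women that attend the Hypertension clinic may be recruited due to their gestational hypertension". Section 3 plans to recruit women who have GH together with gestation-matched normotensive women, and section 6.1 says newly diagnosed women from hypertensive clinics will be recruited. Section 3.12, by contrast, allocates women to groups retrospectively, once the pregnancy outcome is documented.
- **Who scans.** Section 3.1 places retinal imaging and ultrasound at "Blood Flow Lab), Ninewells Hospital, by PI", and the assessment text under section 3.5 repeats this. Section 5.1 says "Study assessments will be conducted by the PI and a trained research member of the team under the supervision of the CI".
- **How the Doppler is obtained.** Under section 3.5 the operator identifies the artery on colour flow, after which "pulsed-wave Doppler will be employed to document three to five similar waveforms".
- **What the team knows.** Section 5.1 has the research team record diagnosis, medications and treatment.

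No section says that the operator or the reader is unaware of GH status, or that measurements are finished before outcome is documented.

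**The concern.** A person who knows that a woman has GH, and who expects GH to go with endothelial dysfunction (the hypothesis in section 2), may without intending it choose frames, vessel positions or waveforms that fit the expectation. A shift that depends on group does not average out. It appears as a group difference, and with 11 women per group there is little information against which to detect it. Pulse-wave Doppler is listed as a primary outcome measure in the synopsis and in Table 1, so the manual step touches a primary comparison. If the section 4 sentence stands, readers will take the measurements as protected when no protection is described.

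**Working it through.** The protocol attaches no figure to its low-bias statement, so there is none to reproduce. The main check is textual; a short calculation then shows what might be at stake.

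**Step 1: what each reason covers.**

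- Diagnosis by attending clinicians keeps the research team from deciding who is a case. It does not affect how an artery is located or which waveforms are kept.
- Objectivity and automation would protect measurement where they apply. Section 4 claims automation only for most tests. The ophthalmic Doppler is described as a manual procedure with two judgement steps: finding the artery and documenting a few similar waveforms.

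**Step 2: whether the operator or reader can know the group.**

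- *Woman recruited because of GH* (sections 3, 3.2, 6.1): yes, at acquisition and at measurement. The principal investigator scans, may take consent (section 3.6), and belongs to the team that records diagnosis.
- *Woman scanned before any diagnosis* (section 3.12): not at acquisition. At measurement it depends on timing, because the protocol does not require reading to be complete before outcome is documented.
- *Biomarkers*: assayed by a core facility (section 3.5), so less exposed.

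**Step 3: illustration of size.**

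Inputs from the protocol: n = 11 per group and a 5% significance level (section 6.1), and the t-test (section 6). Two-sided testing and normal data are assumed. Also assumed, because the protocol gives neither, are a reading shift of b SD and the number k of the 11 cases to whom it applies.

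The apparent mean difference created by the shift is (k/11) × b. For b = 0.5:

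- k = 11: (11/11) × 0.5 = 0.50 SD
- k = 6: (6/11) × 0.5 = 0.27 SD
- k = 3: (3/11) × 0.5 = 0.14 SD

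The false-positive rate was found by simulating 20,000 trials with no true difference, adding b to k cases and counting p < 0.05:

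| Cases affected | b = 0.25 | b = 0.5 | b = 0.75 | b = 1.0 |
|---|---|---|---|---|
| 11 of 11 | 8.5% | 20% | 39% | 61% |
| 6 of 11 | 6.1% | 8.8% | 13% | 19% |
| 3 of 11 | 5.4% | 5.5% | 6.7% | 7.6% |

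A separate run of 60,000 trials at b = 0.5 gave 20.0%, 8.7% and 5.8% for 11, 6 and 3 affected cases. The Mann-Whitney test, which section 6.1 uses for the sample size, gave slightly lower rates: at b = 0.5, 18.8%, 8.1% and 5.2%.

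**The case against.** Several counter-arguments have weight.

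- **Retrospective grouping already masks many scans.** This stands for acquisition. Section 3.5 schedules visits at 10 and 20 weeks, each within 3 weeks, and section 9.1 defines GH as new onset after 20 weeks. On that schedule only scans between 20 and 23 weeks could follow a diagnosis. However, Table 1 and sections 3.2 and 3.14 refer to mid-to-late pregnancy, and sections 3, 3.2 and 6.1 plainly admit women already diagnosed. The protection is therefore partial.
- **A reader might infer that one person doing every scan is the fault.** The documents do not support that. Section 5.1 adds a trained team member to the principal investigator named in section 3.1, and these statements need reconciling. A single operator also removes between-operator variation. The weakness is that group can be known and nothing masks it.
- **A reader might infer that a small tilt would be enough to create the primary finding.** That is not shown. The 20% rate requires all 11 cases to be affected by half an SD; with 3 affected, the rate hardly moves.
- **Only most tests are claimed to be automated, so one manual test is no contradiction.** This is literally true, and the protocol does not show that retinal measurement is operator-dependent. But the conclusion drawn in section 4 is general and covers a primary outcome obtained by hand.
- **Offline coded reading does not mask acquisition.** Correct. With so few women, a reader who did the scans may also recognise some of them. The procedure reduces the risk without removing it.
- **The study is meant to inform future power calculations** (section 3.5). This limits the consequences of an error, but a biased difference would carry over into those calculations.

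**Conclusion.** The concern holds in limited form. The low-bias statement in section 4 is not supported for measurement, chiefly for the ophthalmic Doppler in women whose GH is known, and for any image or waveform read after outcome has been recorded. It is not evidence that bias will occur, and its size cannot be fixed from the protocol. Under an assumed 0.5 SD shift, the false-positive rate runs from close to nominal (5.5-6%, 3 cases affected) through about 9% (6 cases) to about 20% (all 11). These figures assume normal data, a constant shift and no true difference. The weakness should be corrected because it can be reduced cheaply, not because a large effect has been demonstrated.

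**What to change.** 1. Store retinal images and Doppler clips under a code. Have the same reader measure them offline, in one batch and in random order.
2. Have an existing team member who does not do the reading hold the group key until measurements are locked. Section 5.2 gives about four people with file access; the protocol should name the role.
3. Replace the section 4 sentence with this procedure. State openly that acquisition in women with known GH remains unmasked, and that a reader who did the scans may recognise some of them.
4. Report results separately for scans made before and after GH diagnosis.
5. Reconcile sections 3.1 and 5.1 on who conducts the assessments.

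**Cost.** A coding list, saved Doppler clips and later availability of measurements. Participants already have identification numbers (section 5.1) and retinal images are already uploaded to a computer (section 3.5). No extra visit, procedure, participant or reader is needed.
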